### 7.4 Criteria for withdrawal / discontinuation of participants

Participants are allowed to withdraw from the study at any time and for any reason. They do not have to share the reasons with the investigator. They will be asked to return the IMD. If the decision is made by the investigator then they will inform the participant in person that they are no longer needed for the study. Reasons for withdrawing a participant from the study could be for non-compliance during testing, unreliable responses, medical reasons such as an ear infection, or the study may need to be stopped or postponed. Any data gathered from these subjects will be used for the current study. All data will remain encoded because results are only recorded using the identification code of the subject. There are normally at least five "back-up" test participants on the list to replace those that withdraw or are withdrawn. These are participants that have already been screened and determined to be appropriate for the testing.

## 8. STUDY INTERVENTION

### 8.1 Identity of Investigational Products (medical device)

The treatment will be approximately 4 months of use with the IMD and breaks in between when they will return to the RMD. All participants will already be Bernafon hearing aid users; therefore, during the investigation they will stop using RMD and switch to the IMD for the assigned periods.

Additionally, there will be lab tests in which the participants will use the IMD for up to 2 hours at a time during testing in the clinic.

There are 3 field tests planned. In between each field test they will return to wearing RMD. At the end of the entire trial, and once the devices have been CE marked, the participants will have the choice to continue wearing the RMD or to switch and wear the IMD permanently.

#### 8.1.1 Experimental Intervention (medical device)

The investigational product (IMD) is a medical device. It is a new version of a Bernafon hearing device. The name is [REDACTED]. It does not significantly deviate from the current commercial product. The hearing aid still has the same intended use and the basic function of amplifying sound. The IMD uses a new chip to power the hearing aid. Performance is expected to be the same or better than the RMD. They are non-invasive devices. The hearing aid is worn behind/over the ear with a part that fits into the ear canal. The part that fits in the ear canal is either made of silicon or plastic that is covered with an acrylic coating (for custom molds). The hardware of the BTE is painted with a non-toxic paint.

Figure 1: [REDACTED] device

#### 8.1.2 Control Intervention (comparator treatment / medical device)

The Reference Medical Device (RMD) is called [REDACTED] and is a CE marked hearing aid. Its intended purpose is the same as [REDACTED] - to amplify sounds. The strength of the amplification is programmed according to the subject's individual hearing loss. There is no placebo treatment used during this study. The RMD and the IMD will be programmed based on the subject's individual hearing loss. The amplification will be the same from both devices with +/- 5 dB. The output amplification will be tested for both the RMD and the IMD to ensure that they are similar.

#### 8.1.3 Packaging, Labelling and Supply (re-supply)

The IMD is labelled by printing the name of the device directly onto the device. There is an individual serial number printed in the battery drawer that identifies each specific device. Additionally the device comes in a blister pack that includes a small paper with the serial number, name and description of the device (style and color). The blister is removed by the healthcare professional, and the device is placed in plastic case for the subjects. The packaging and labelling are the same for both the IMD and the RMD (marketed) device.

#### 8.1.4 Storage Conditions

The devices are stored in the blister packs which are kept in boxes in a warehouse until shipped. They have a shelf life of years. The IMD and the RMD are stored in exactly the same way. They should not be exposed to temperatures below -25° and not above 60° Celsius during storage or transport. The storage is the same as for devices already in use. The storage of these devices is according to standard procedures.

### 8.2 Administration of experimental and control interventions

#### 8.2.1 Experimental Intervention

The devices are worn over the ear with a piece that is worn in the ear. They are non-invasive. The RMD will have been worn for at least 6 months as all subjects are current hearing aid users. The amplification is prescribed based on the subject's hearing loss. Both the RMD and the IMD will provide the same amount of amplification. The IMD will be worn for at least 2 weeks per field test period in order to give the subjects enough time to wear the devices in various sound environments. They need to wear the device in different environments to make a comparison between the IMD and the RMD. The questionnaires ask questions about specific environments, and it's beneficial if the subject has experienced most of them. Normal use of a hearing device is 8-10 hours per day. The subjects will wear the IMD for the amount of time during the day that they wear RMD. They will not be told how long to wear it. The device should be worn as the subjects normally wear their current device (RMD).

The study procedure will use a single group assignment design in which the subjects will wear the IMD at the same time. Use of a new feature will be randomized so that some start the trial with it and some without it. As stated previously, the device is non-invasive and requires no surgical procedure. The device will be inserted into the ear and placed over the ear each morning by the subjects themselves and removed each night by the subjects themselves. There is minimal training needed for a first time user to learn how to insert a hearing device. The test subjects will have been wearing the RMD for at least 6 months; therefore, they will not need additional training. The IMD is inserted in the same manner at the RMD. The subjects will be given an Instructions for Use booklet that explains how to insert the device and provides further instructions concerning cleaning, battery changing, and warnings.

#### 8.2.2 Control Intervention

The RMD is the current device that the test subjects are using. They will have used the device for at least 6 months so that they are experienced with using hearing aids. They will interrupt the use of the RMD during the field trial periods to use the IMD. They need to wear the device in different environments to make a comparison between the IMD and the RMD. The questionnaires ask questions about specific environments and it's beneficial if the subject has experienced most of them. Normal use of a hearing device is 8-10 hours per day. The subjects will wear the IMD for the amount of time during the day that they wear the RMD device. They will not be told how long to wear it. The device should be worn as the subjects normally wear the RMD.

The study procedure will use a single group assignment design in which the subjects will wear the IMD at the same time. Use of a new feature will be randomized so that some start the trial with it and some without it. As stated previously, the device is non-invasive and requires no surgical procedure. The device will be inserted into the ear and placed over the ear each morning by the subjects themselves and removed each night by the subjects themselves. There is minimal training needed for a first time user to learn how to insert a hearing device. The test subjects will have been wearing the RMD for at least 6 months; therefore, they will not need additional training. The IMD is inserted in the same manner at the RMD. The subjects will be given an Instructions for Use booklet that explains how to insert the device and provides further instructions concerning cleaning, battery changing, and warnings.

### 8.3 Dose / Device modifications

The IMD will provide the same amplification as the subjects' RMD; therefore, they should not experience any significant negative differences that would make the subjects want to discontinue use of the device. If a subject reports certain differences that can be improved with fine tuning, for example, of amplification, this step will first be taken to see if the situation improves enough for the subject to continue with the trial. However, if the subject requests to discontinue they can immediately remove the IMD and return to the RMD. They will be asked to return the IMD to Bernafon AG, but their data will still be included in the results for the current study. All data will remain encoded because results are only recorded using the identification code of the subject.

#### **8.4 Compliance with study intervention**

It is clearly explained to the subjects that during the periods of intervention it is important to the study that they only wear the IMD. However, the RMD are left in their possession in the event that the IMD does not work or if they find that they simply can't hear as well with the IMD as the RMD. For safety reasons the RMD are left with the subjects to use in the event that the IMD does not work. For ethical purposes, the subjects must have a back-up solution for their hearing impairment.

The software monitors the amount of time that the devices are worn. Therefore, it will be noted if the IMD has not been worn a standard or expected amount of time. If the device has not been worn a sufficient amount of time the data will not be used for the study. The subjects will be asked to return the devices.

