Objective(s):	The purpose of this research is to show that the performance of the device is as good as or better than the current device or previous hearing aid generation. Furthermore, speech should not be negatively affected with the addition of the new feature, the usability of the devices (that end users are able to handle the devices) should be as good as the current device, and there should be no artefacts or unwanted noises. Some measurements serve as quality control prior to product launch.

Outcome(s):	
Primary Endpoint:
 

Primary Outcome is the speech intelligibility with the investigational device compared to the current device (using speech tests)

 
Secondary Endpoints:
 

Comparing the subjective performance of the investigational device to the current device (using questionnaires)

Speech intelligibility with the new feature on and off (using speech tests)

Handling/usability of the devices (specified questionnaire)

Subjective preference testing (using interviews)

Procedural safety meaning that there are no unwanted noises or artefacts heard from the devices (as reported by the subjects)

 
Scores from speech tests and questionnaires should be as good as or higher than with previous devices. Handling of the devices should be the same or easier than previous devices. No unexpected, unwanted behaviour from the devices should occur.

Study design:	This is a controlled, open label, comparative clinical investigation conducted monocentric at the premises of Bernafon in Bern, Switzerland.

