### 4.2 Primary Objective

The study seeks primarily to determine if the performance of the IMD is as good as the RMD. As a second primary objective the study seeks to proactively determine if there is any unknown and/or unwanted behavior from the IMD. The study seeks to validate that the performance of the IMD is as expected in comparison with the RMD, meaning that the performance of the IMD should not be inferior to the RMD.

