#### **8.5 Data Collection and Follow-up for withdrawn participants**

Withdrawn subjects' data will not be used in any final data analysis or report. Any data that is collected prior to withdrawal will be kept in the data management database. The data will remain encoded because results are only recorded using the identification code of the subject. Withdrawn subjects will have the same follow-up as those subjects that complete the trial. They will already be Bernafon hearing aid users and, therefore, welcome to return to the clinic for follow-up fine tuning and maintenance as needed.

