## 10. SAFETY

### 10.1 Medical Device Category C studies

All adverse events (AE) including all serious adverse events (SAE) are collected, fully investigated and documented in the source document and appropriate case report form (CRF) during the entire study period, i.e. from patient's informed consent until the last protocol-specific procedure, including a safety follow-up period. Documentation includes dates of event, treatment, resolution, assessment of seriousness and causal relationship to device and/or study procedure.

The information on AEs is systematically collected by the clinician at each study visit. They will follow the procedures outlined in SOP-Medical Device Incident Reporting. The subjects are asked to keep a diary and write down any unexpected events. During the regular clinic visits the subjects are then asked questions about the event to gather details and to determine the severity of the event. If a subject reports pain that results in the inability to use the device he will be withdrawn from the study in order to avoid any pain from using the device and to remove partial data from the study. For reports of pain caused by insertion or the dome itself, the problem can be addressed in the clinic. For example, a different style or size of dome can be placed on the hearing aid, and re-training of insertion can be performed with the subject to avoid wrong or forceful insertion of the device. For reported pain they will be advised to not wear the device for 24 hours before resuming use.

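### Protocol 8.4, 8.5, 10.1 and 11.5, contradicted by 7.4 and 8.3, can drop participants with IMD failure or disabling pain from the final report on unwanted IMD behaviour; no safety set is defined

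*Protocol*

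**What the plan says.** **The objective.** Protocol 4.2 states: "As a second primary objective the study seeks to proactively determine if there is any unknown and/or unwanted behavior from the IMD". The synopsis lists freedom from unwanted noises and artefacts as a secondary endpoint and adds the expectation "No unexpected, unwanted behaviour from the devices should occur". Sections 5.4 and 9.2.4 name the effects of interest, among them discomfort, muting or shut-off, artefacts and loud sounds, captured by diary.

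**Rules that take data out.**
- 8.4, wear time: "If the device has not been worn a sufficient amount of time the data will not be used for the study". No threshold is given, and 8.2.1 says of wearing time "They will not be told how long to wear it". The same section explains the fallback device: "For safety reasons the RMD are left with the subjects to use in the event that the IMD does not work".
- 8.5, withdrawal: "Withdrawn subjects' data will not be used in any final data analysis or report".
- 10.1, pain that makes the device unusable: the participant is withdrawn "in order to avoid any pain from using the device and to remove partial data from the study".
- 11.5: complete cases only.
- 11.4.1: one analysis population, the per-protocol set.

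**Rules that keep data in.** Section 7.4 says data gathered from withdrawn participants, including those withdrawn for medical reasons, will be used. Section 8.3 says a participant who asks to stop and goes back to the RMD still has their data included.

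**Safety.** Section 11.4.5 rests the safety analysis on interviews and clinical judgement by the principal investigator. It states no population, count or denominator. The SAP contains no safety analysis and no analysis sets.

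**The concern.** An IMD that shuts off, fails or hurts is the kind of event the second primary objective is meant to find. It is also the kind of event that leads a participant to wear the IMD less, stop or be withdrawn. If the exclusion rules are followed as written, the reason for leaving the analysis can be the outcome itself, and the error can only favour the IMD.

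The synopsis expects no unwanted behaviour at all. Against such a criterion, omitting even one affected participant can change the conclusion, and the study is described in 4.1 as the final validation before release for sale. Because the text also contains the opposite instructions, someone must choose between them, and nothing prevents that choice from being made after the events are known.

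**Working it through.** The documents state no figure for this point: no expected event rate, no number of exclusions and no planned safety proportion. The only sample-size figure, 24, belongs to the SRT test. It reproduces with the SAP's inputs: (2 × (1.960 + 1.282) / 1.34)² = 23.4, rounded up to 24. It says nothing about safety.

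**1. Sections side by side**

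| Situation | Excluded by | Included by |
|---|---|---|
| IMD fails or is worn little, participant stays enrolled | 8.4, if wear is judged insufficient; 11.5, if data are incomplete | no section |
| Participant asks to stop and returns to the RMD | 8.5 if treated as withdrawn; 11.5 | 8.3, 7.4 |
| Pain prevents use, participant is withdrawn | 10.1, 8.5, 11.5 | 7.4 |
| Dome or insertion pain | not excluded by itself: "For reports of pain caused by insertion or the dome itself, the problem can be addressed in the clinic" | stays in |

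No entry in the exclusion column distinguishes safety data from SRT or questionnaire data. Section 8.5 covers both analysis and report.

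**2. What is captured regardless.** Section 10.1 has all adverse events recorded from consent to the last procedure. Section 10.1.2 sends SAEs, health hazards and device deficiencies to the sponsor within 24 hours, and 10.1.1 counts a malfunction as a device deficiency. Section 12.1.2 requires a CRF for non-completers, with the reason for withdrawal. Section 8.5 keeps data collected before withdrawal in the database. So the events are recorded. What is not secured is their place in the final analysis and report.

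**3. Illustration of size.** Inputs: N = 35 (synopsis, approximate); the event count is an assumption. Exact (Clopper-Pearson) limits for k of n are the 2.5% quantile of Beta(k, n−k+1) and the 97.5% quantile of Beta(k+1, n−k).
- All kept: 3/35 = 8.6%; limits from Beta(3, 33) and Beta(4, 32) give 1.8 to 23.1%.
- All three excluded, no event among the rest: 0/32; upper limit 1 − 0.025^(1/32) = 10.9%.

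**4. When only some are excluded.** Let p be the share of participants affected and q the share of those whose data are excluded. The chance that at least one affected participant remains in the analysed data is 1 − (1 − p(1 − q))^35. All values of p and q are assumptions.

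| p | q = 0 | q = 0.5 | q = 0.8 | q = 1 |
|---|---|---|---|---|
| 3% | 0.656 | 0.411 | 0.190 | 0 |
| 5% | 0.834 | 0.588 | 0.297 | 0 |
| 10% | 0.975 | 0.834 | 0.507 | 0 |

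The column q = 0 is what a safety set of all fitted participants would give.

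**The case against.** The strongest reply is that removal is not the settled rule. Sections 7.4 and 8.3 say plainly that data from withdrawn and discontinuing participants are used. This stands, and it rules out the inference that affected participants are certain to be removed. It does not make the plan safe: 7.4 and 8.5 give opposite instructions for the same people, and 8.3 does not reach a participant who stays enrolled with low wear.

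Second, a reader might infer that any return to the RMD or any report of pain removes the participant. The text does not say so. Fallback matters only if wear is then judged insufficient, and only pain that prevents use leads to withdrawal.

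Third, a reader might infer that the events disappear from the study. They do not, as the recording and reporting duties in 10.1, 10.1.2 and 12.1.2 apply whatever the participant's status. Related or possibly related SAEs also go to the ethics committee and Swissmedic within 7 days. The gap is confined to the final analysis and report.

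Fourth, 11.4.5 plans interviews and judgement during the trial, not a proportion, so 0 of 32 is not an output the plan defines. That is fair, and the figure is an illustration. It also depends on every affected participant being excluded and no retained one reporting anything, although effects such as whistling or occlusion need not stop use.

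Fifth, the synopsis ranks this endpoint as secondary, against 4.2. The gap exists under either label.

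**Conclusion.** The concern holds in this form: the plan contradicts itself on whether data from these participants are used. Under 8.4, 8.5, 10.1 and 11.5 it can leave out of the final report the people in whom unwanted IMD behaviour occurred. With only a per-protocol set and no stated safety population, nothing protects that objective. Any resulting bias favours the IMD.

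The size cannot be derived from the documents. The change from 8.6% (1.8 to 23.1%) to 0 of 32 (0 to 10.9%) assumes 35 participants, 3 affected, all 3 excluded and no other events; the table of partial exclusion shows smaller effects.

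Two further inferences are tempting and unsupported. The gap between about 35 enrolled and 24 required (11 of 35, 31%) is the surplus over the SRT sample size and does not measure safety loss. Nor do the documents make a return to the RMD because of poorer hearing an unwanted-behaviour event: it is not in the lists in 5.4 and 9.2.4, and it overlaps the performance outcome.

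**What to change.** 1. In 11.4.1 and 11.4.5, define a safety set of every participant fitted with an IMD at least once. Report AE/ADE, device-deficiency, diary and interview safety data on it, whatever the wear time, withdrawal or completion. Carry the same definition into the SAP.
2. In 8.4, 8.5, 10.1 and 11.5, limit the exclusions to the SRT and questionnaire analyses, and reconcile them with 7.4 and 8.3 so that one data-use rule remains.
3. List every exclusion and every return to the RMD with its reason.
4. State the same rank for this objective in 4.2 and the synopsis.

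The clinical withdrawal rule is untouched. The cost is mainly wording, because adverse events, diary and interview results already have CRF fields and 12.1.2 already asks for the reason for withdrawal. The CRF list in 12.1.1 shows no field for wear time or for the reason for a temporary return to the RMD, so item 3 needs a small amount of extra listing work. The remaining downside is a possibly less favourable safety report.

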#### **8.5 Data Collection and Follow-up for withdrawn participants**

Withdrawn subjects' data will not be used in any final data analysis or report. Any data that is collected prior to withdrawal will be kept in the data management database. The data will remain encoded because results are only recorded using the identification code of the subject. Withdrawn subjects will have the same follow-up as those subjects that complete the trial. They will already be Bernafon hearing aid users and, therefore, welcome to return to the clinic for follow-up fine tuning and maintenance as needed.

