#### **11.5 Handling of missing data and drop-outs**

For missing data, the PI will contact the involved subject to evaluate the possibility of getting missing data from a questionnaire by post. If a test subject cannot come to the evaluation visit, after exhausting all the possibilities to reschedule a new one, the devices will be sent back per post. If a subject does not want to adhere to the protocol, he can easily switch back to his own device (RMD) and return the IMD.

Data will be immediately removed if the PI has some doubts about the data accuracy (especially about the understanding of the APHAB questionnaire).

Dropouts will not be replaced; therefore, extra subjects over the calculated sample amount will be included from the beginning to ensure enough completed cases with all data.

Analysis will be done on the complete case only.

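### The protocol both uses and bars withdrawn participants' data, and its only analysis set rests on undefined removal rules with no planned check for selection

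*Protocol*

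**What the plan says.** **Use of data after withdrawal.**
- Protocol 7.4, on participants who leave or are taken out of the study: "Any data gathered from these subjects will be used for the current study".
- Protocol 8.3, on participants who ask to stop using the investigational device (IMD): "their data will still be included in the results for the current study".
- Protocol 8.5, on withdrawn participants: their "data will not be used in any final data analysis or report". Data collected before withdrawal stay in the database.
- Protocol 10.1, on participants whose pain prevents use of the device: one stated purpose of withdrawing them is "to remove partial data from the study".

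**Replacement.** Section 7.4 describes back-up "test participants on the list to replace those that withdraw or are withdrawn". Section 11.5 says "Dropouts will not be replaced" and relies on over-enrolment instead.

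**Removal of data from participants who stay.** Section 8.4: "If the device has not been worn a sufficient amount of time the data will not be used for the study". Section 11.5: "Data will be immediately removed if the PI has some doubts about the data accuracy", with particular mention of the APHAB.

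**Analysis set.** Sections 11.3 and 11.4.1 name a per-protocol set and a single analysis, and 11.5 restricts it to complete cases. ITT appears only in the abbreviation list. The SAP says nothing on analysis sets, withdrawals, wear time or missing data.

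**The concern.** Two analysts who each follow the protocol could analyse different participants. That is a defect whatever the results turn out to be.

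The second problem is selection. Section 8.4 leaves participants their reference device (RMD), among other reasons in case they hear less well with the IMD, and then discards data when the IMD was worn too little. Low wear can therefore be a consequence of poor IMD performance. If such participants attend Visit 6, they have a valid RMD–IMD pair of SRTs from one laboratory session, and removing it would move the mean difference towards non-inferiority. Because only one analysis set is planned, no planned result would show whether the removals mattered.

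Third, 8.5 read literally leaves withdrawn participants out of the final safety account, although 4.2 makes detection of unwanted IMD behaviour a second primary objective.

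**Working it through.** **1. Can the rules be read together?** Sections 7.4 and 8.5 cover the same group and give opposite instructions, so they cannot. Section 8.3 could be read as stopping the device rather than leaving the study, but the conflict between 7.4 and 8.5 stands without it. On replacement, 7.4 and 11.5 also give opposite instructions.

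**2. Which rules can reach the primary endpoint?** The defining SRT comparison is made once, at Visit 6 (9.2.1, 9.3.6, 11.4.2).
- Participants who leave earlier have no primary value. For them the primary issue is missing data, and the conflict between 7.4 and 8.5 bears on questionnaire, feature and safety results.
- Participants with a Visit 6 pair can be removed under 8.4 or by PI doubt under 11.5. Section 8.4 gives neither a cut-off nor the scope of the data to be discarded. The PI's stated blinding (6.2.2) covers only the two IMD sets, not IMD versus RMD.

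**3. The plan's own figure.** The sample size uses n = sd²(z₁₋α + z₁₋β)²/δ² with sd 2, one-sided α 0.025 and power 90%.
- With the unrounded SAP margin, 2 − 1.31/2 = 1.345: 4 × (1.960 + 1.282)²/1.345² = 23.23, so 24, as stated.
- With 1.3: 24.87, so 25.

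The present point does not alter this figure. About 35 are to be enrolled, so 35 − 24 = 11 participants (31%) could be lost with the target still met.

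**4. Illustration: pairs that exist but are removed.** The number removed (k) and the correlation (ρ) are assumptions; the documents give neither. Individual differences C − T are drawn from a normal distribution with mean −1.3 dB (the null boundary) and SD 2 dB, n = 35. The score is ρ·z(d) + √(1−ρ²)·noise, where z(d) is the standardised difference. The k lowest scores are dropped, and a one-sided 2.5% t-test of mean > −1.3 is applied, with 200,000 trials per scenario. Rate of declaring non-inferiority:

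| k removed | ρ = 0 | ρ = 0.1 | ρ = 0.3 | ρ = 0.5 |
|---|---|---|---|---|
| 1 | 2.5–2.6% | 2.7% | 3.2% | 3.9% |
| 3 | 2.5–2.6% | 3.1% | 4.7% | 7.1% |
| 5 | 2.5–2.6% | 3.4% | 6.2% | 11.0% |

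For ρ from 0.3 to 0.5 the mean shifts by 0.10–0.16 dB (k = 3) and 0.15–0.25 dB (k = 5). The retained SD hardly changes: at k = 3 it averages 1.98, 1.96 and 1.92 dB for ρ = 0, 0.3 and 0.5.

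**5. Illustration: participants with no Visit 6 SRT.** Let m of 35 be missing, with an assumed observed mean and SD 2 dB. Give all m the same value x and find the x at which the lower 95% limit for n = 35 equals −1.3, with the SD recomputed.

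Example with m = 3 and observed mean −0.5 dB:
- Observed lower limit: −0.5 − 2.040 × 2/√32 = −1.22 dB, so non-inferiority is declared.
- At x = −1.99, the pooled mean is (32 × −0.5 + 3 × −1.99)/35 = −0.628 and the pooled SD is 1.956.
- The lower limit is then −0.628 − 2.032 × 1.956/√35 = −1.30 dB.

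| Observed mean | m = 3 | m = 5 |
|---|---|---|
| −0.5 dB | −1.99 dB | −1.57 dB |
| 0 dB | −5.37 dB | −3.67 dB |

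Non-inferiority is lost if the missing participants average the tabulated value or worse.

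**The case against.** The strongest case against runs as follows.
- **The contradiction barely touches the primary endpoint.** Anyone who withdraws before Visit 6 has no primary SRT under either rule. This is correct, and it limits the withdrawal conflict mainly to other outcomes.
- **The wear-time rule may mean only that period's field data.** Section 8.4 concerns the intervention periods, and 8.2.1 gives benchmarks: at least two weeks per period, and daily wear like the participant's own RMD use. The narrower reading is possible, but the text does not require it, and benchmarks are not an exclusion threshold.
- **PI doubt is aimed at the APHAB.** Mainly so, but the rule is not limited to it. No text ties this removal to IMD performance.
- **Removals are traceable.** The audit trail (12.2.2), retained data (8.5), recorded withdrawal reasons (12.1.2) and deviation reporting (11.4.6) all help. They allow a reconstruction but do not plan an analysis.
- **The magnitudes are invented.** The values of k and ρ are indeed assumptions, and the error rates apply at a true deficit of 1.3 dB, whereas the plan expects similar performance.
- **The study is called exploratory.** It nevertheless states a formal non-inferiority hypothesis and margin, and 1.1 says the sponsor will use the results to prove performance.
- **Safety collection continues.** Adverse events are collected from consent and serious ones reported (10.1, 10.1.2). The safety point therefore rests on a literal reading of 8.5 and concerns the final report only.

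**Conclusion.** The concern holds and should be fixed. The textual conflict is certain: 7.4 against 8.5 on data use, and 7.4 against 11.5 on replacement, with nothing in the SAP to settle either. It is also certain that the wear-time rule lacks a cut-off and a scope, and that the sole planned analysis is per-protocol and complete-case.

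Bias in the primary result is possible, not demonstrated. It needs participants with a Visit 6 pair to be removed for reasons correlated with their SRT difference. Under the assumptions above, the error rate runs from no inflation (ρ = 0) to 11.0% (k = 5, ρ = 0.5). Missing Visit 6 values matter mainly if the IMD is somewhat worse. At an observed mean of 0 dB, three missing participants would have to average about −5.4 dB to change the conclusion; at −0.5 dB, about −2.0 dB would do so. The sample size of 24 is unaffected.

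**What to change.** 1. Reconcile 7.4, 8.3, 8.5, 10.1 and 11.5 into one rule on the use of withdrawn participants' data and one rule on replacement. This concerns data use only, not when a participant should be withdrawn.
2. Analyse everyone fitted with an IMD who has both RMD and IMD SRTs, whatever their wear time or missing questionnaires, beside the per-protocol set, and report both. The per-protocol set keeps its purpose, since 3.5 asks for two weeks of wear per period.
3. Add a sensitivity analysis, such as a tipping point, for participants without a Visit 6 SRT.
4. Replace insufficient wear and PI doubt with objective criteria, including which data each one removes, fixed before results by condition are seen. List every removed value with its reason.
5. Report safety for everyone fitted with an IMD, including events up to withdrawal.

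The cost is protocol and SAP wording and one or two analyses of data already collected, with no extra visits or participants. The price is a possibly less favourable or more variable estimate, and two results to interpret if they differ.
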